1.1 Background

Age-related macular degeneration (AMD) is a leading cause of severe vision loss in people, affecting 11.6% to 18.5% of individuals between 60 and 69 years old and 31.6% to 45.3% of individuals between 80 and 84 years old in North America, Europe, and Oceania (Wong et al 2014). Genetic, environmental and health factors play an important role in the pathogenesis of the disease.

AMD is classified into 2 clinical subtypes: the non-neovascular (atrophic) or dry form, and the neovascular (exudative) or wet form (Ferris et al 1984, Lim et al 2012, Miller 2013). Neovascular AMD (nAMD) is characterized by the growth of abnormal new blood vessels (neovascularization) under the retinal pigment epithelium (RPE) or sub-retinal space from the subjacent choroid, termed choroidal neovascularization (CNV) (Ferris et al 1984). These newly formed vessels have an increased likelihood to leak blood and serum, damaging the retina by stimulating inflammation and scar tissue formation. This damage to the retina results in progressive, severe, and irreversible vision loss (Shah and Del Priore 2007, Shah and Del Priore 2009). Without treatment, most affected eyes will have poor central vision (20/200) within 12 months (Blinder et al 2003). Although the neovascular form of the disease is only present in about 10 % of all AMD cases, it accounted for approximately 90 % of the severe vision loss from AMD prior to the introduction of anti-vascular endothelial growth factor (anti-VEGF) treatments (Ferris 1983).

Anti-VEGF in nAMD

Vascular endothelial growth factor (VEGF) has been shown to be elevated in patients with nAMD and is thought to play a key role in the neovascularization process (Spilisbury et al 2000).

The use of intravitreal injection (IVT) pharmacotherapy targeting VEGF has significantly improved visual outcomes in patients with nAMD (Bloch et al 2012, Campbell et al 2012). Intravitreal administration of anti-VEGF treatments is the current standard of care in nAMD.

Treat-and-Extend treatment regimen

Typically, a Treat-and-Extend (T&E) treatment regimen includes a loading phase of monthly injections, followed by a maintenance phase during which the injection interval is progressively prolonged if there is no disease activity (DA), primarily determined by optical coherence tomography (OCT) and visual acuity assessment, or shortened if disease recurs. The T&E treatment regimen aims at identifying optimal individual injection intervals to minimize the number of injections and reduce visit burden while maintaining the vision gains obtained at the end of the loading phase during the maintenance phase. T&E treatment regimen has been approved in the labels of anti-VEGF treatments, such as ranibizumab (Lucentis®) and aflibercept (Eylea®) in Europe and many other countries. The treatment paradigm has come in a variety of regimens.

Whereas most T&E regimens entail extending or shortening the injection interval based on absence or presence of DA, the Treat-to-Control (TtC) regimen emphasizes sustained disease control to determine the optimal treatment interval for each patient rather than solely adjusting treatment intervals. For instance, it allows patients that may not benefit from treatment interval

extension to be temporarily or lastingly maintained on a treatment interval. While T&E regimens have been associated with a reduction in treatment and visit burdens in AMD, the number of visits remain relatively high for most patients as the average number of injections in Lucentis® and Eylea® studies range from 8 to 10.1 in the first 12 months and from 10.4 to 18.6 in the first 2 years (Wykoff et al 2015, DeCroos et al 2017, Wykoff et al 2017, Guymer et al 2018, Silva et al 2018, Gillies et al 2019, Kertes et al 2019, Ohji et al 2020).

There still is a need for highly effective treatments that prolong intervals between injections and further reduce treatment burden, while maintaining vision gains.

Brolucizumab

Brolucizumab (RTH258, ESBA1008, AL-86810), is a humanized single-chain antibody fragment (scFv) with a molecular weight of ~26 kilodalton (kDa) which inhibits VEGF-A binding to its receptors VEGFR1 and VEGFR2. Brolucizumab is administered by intravitreal injection and has been approved by the US Food and Drug Administration on 7 Oct 2019 and many other countries (e.g. EU countries, Australia, Japan and Canada) subsequently, for the treatment of nAMD.

The efficacy and safety of brolucizumab in subjects with nAMD has been demonstrated in two Phase III pivotal studies (RTH258-C001 [HAWK] and RTH258-C002 [HARRIER]). nAMD patients received brolucizumab every 12 weeks (q12w), with the option of adjusting to a q8w dosing interval based on DA, or aflibercept q8w, after three monthly loading doses. Brolucizumab was non-inferior to aflibercept with regards to change from Baseline in BCVA at week 48, with over half of the participants in the brolucizumab 6 mg arm maintained exclusively on the q12w dosing interval (56% in HAWK and 51% in HARRIER). Significantly fewer patients in the brolucizumab 6 mg arm had DA at Week 16 in a head-to-head comparison based on a matching dosing intervals, with a relative decrease of 30% (P = 0.0022) versus aflibercept. Significantly fewer patients on brolucizumab had intraretinal fluid (IRF) and/or subretinal fluid (SRF), with a 35% and 33% reduction relative to aflibercept at Week 16 (P < 0.001 for both) in HAWK and HARRIER, respectively, and a 31% and 41% reduction relative to aflibercept at Week 48 in HAWK and HARRIER, respectively (P < 0.0001 for both). These advantages for brolucizumab were maintained in the second year. Safety was comparable between the treatment arms over 2 years.

Since the first marketing authorization approval in October 2019 for the treatment of nAMD, adverse events of retinal vasculitis and/or retinal vascular occlusion, that may result in severe vision loss and typically in the presence of intraocular inflammation, have been reported from post-marketing experience with brolucizumab (Beovu®).

Results of the mechanistic study BASICHR0049 of blood samples from nAMD patients exposed to brolucizumab and having subsequently developed Retinal Vasculitis (RV) and/or Retinal Vascular Occlusion (RO), taken together with accumulated data of the association of treatment-emergent immunogenicity and intraocular inflammation (IOI) indicate a causal link between the treatment-emergent immune reaction against brolucizumab and the brolucizumab-related “retinal vasculitis and/or retinal vascular occlusion, typically in the presence of IOI”. This finding supports the requirement to discontinue treatment with brolucizumab in patients who develop events of RV and/or RO.

In addition, based on the USM (CRTH258AUS04 first interpretable results [FIR]), the interval between two brolucizumab doses should not be shorter than 8 weeks beyond the loading phase.

These impacts on the risk/benefit balance of the product are considered to be low and the overall risk/benefit assessment remains positive, when patients are dosed at q8w or longer after the loading phase and when patients who develop RV and/or RO are discontinued from further treatment with brolucizumab.

For further details, please refer to the investigator brochure (IB) or package insert whichever is applicable.

CRTH258A2303 study (TALON)

There is an ongoing study CRTH258A2303 (TALON) which intends to complement the current clinical dataset on brolucizumab by generating new evidence based on the T&E concept prevalent in the current management of patients with nAMD. It will be comparing the efficacy and safety of brolucizumab and aflibercept administered in three monthly injections at Baseline, Week 4, and Week 8 (loading phase), followed by an identical 4-week-adjustment Treat-to-Control regimen with treatment intervals from 8 to 16 weeks. Subjects requiring injections every 4 weeks after the loading phase will be discontinued from further study treatment.

This study, CRTH258A2303E1, is an extension study of the CRTH258A2303 (TALON) study, aiming at gathering additional long-term efficacy and safety evidence about brolucizumab in a TtC treatment regimen with treatment intervals further extended up to 20 weeks in nAMD. It intends to contribute to the growing clinical dataset of brolucizumab by generating supplementary evidence on treatment safety, efficacy, and durability in nAMD.

1.2 Purpose

The purpose of this study is to evaluate the efficacy and safety of brolucizumab used in a Treat-to-Control (TtC) regimen with maximum treatment intervals up to 20 weeks for the treatment of patients with neovascular age-related macular degeneration (nAMD) who have completed the CRTH258A2303 study (TALON).

In addition, switch data from aflibercept to brolucizumab is collected.

2 Objectives and endpoints

Table 2-1 Objectives and related endpoints

Objective(s)	Endpoint(s)
Primary objective(s)	Endpoint(s) for primary objective(s)

To evaluate the extended durability of brolucizumab in a TtC regimen with respect to the duration of treatment intervals at Week 56	
Duration of the last interval with no DA up to Week 56

To evaluate the functional outcomes of brolucizumab in a TtC regimen with respect	
Change in BCVA from extension baseline at Week 52 and Week 56

Objective(s)	Endpoint(s)
to average change in BCVA at Week 52 and Week 56	
Secondary objective(s)	Endpoint(s) for secondary objective(s)

 To evaluate the anatomical outcomes of brolocizumab in all patients and per randomized arm in the core study To assess the durability of brolocizumab in all patients and/or per randomized arm in the core study To assess the functional outcomes of brolocizumab per randomized arm in the core study To assess the safety of brolocizumab 	
 Change in CSFT from extension baseline to Week 52 and Week 56 Number of visits with presence of IRF and/or SRF, and sub-RPE fluid in the central subfield, as assessed by SD-OCT at Week 52 and Week 56 Duration of the last interval with no DA up to Week 56 Duration of the maximal intervals with no DA up to Week 56 Change of the duration of last interval with no DA between extension baseline and Week 56 Change in BCVA from extension baseline to Week 52 and Week 56 Occurrence of Ocular and Non-ocular AEs up to Week 56

2.1 Primary estimands

There are two primary clinical questions of interest: 1. what is the effect of brolocizumab 6 mg on treatment interval extension? and 2. what is the effect of brolocizumab 6 mg on visual acuity change in a TtC regimen with maximum treatment intervals up to 20 weeks after treatment in patients with nAMD who have completed the CRTH258A2303 study?

These two effects were targeted to estimate the effect of brolocizumab in a TtC regimen with maximum treatment intervals up to 20 weeks without breaking masking of the CRTH258A2303 study (TALON).

The primary estimand is described by the following attributes:

1. Population: participants who have completed the CRTH258A2303 study (TALON) irrespective of the study treatment received in the core study. Further details about the population are provided in [Section 5](#).

2. The co-primary variable 1 is change in BCVA from extension baseline at Week 52 and Week 56, i.e. the average change in BCVA from extension Baseline to Week 52 and Week 56. The co-primary variable 2 is the duration of the last interval with no DA up to Week 56, i.e. the proportion of participants in q4w, q8w, q12w, q16w and q20w intervals (interval distribution) at last interval with no DA up to Week 56 (subjects who will be assigned to a 4-week interval will be analyzed as such, but discontinued from further study treatment).

3. Treatment of interest: brolocizumab 6 mg will be taken for the entire study duration. Further details about the investigational drug are provided in [Section 6](#).

Handling of remaining intercurrent events:

- Study treatment discontinuation: For the co-primary endpoint of change in BCVA, a hypothetical treatment strategy will be applied to estimate the treatment effect under the hypothetical assumption that the patient would not start an alternative anti-VEGF treatment (i.e. standard of care therapy) on the study eye. For the co-primary endpoint of duration of treatment interval, a ‘while on treatment strategy’ will be applied as disease stability assessment will not be performed after the patient discontinued treatment.
- Study treatment interruption: For both the co-primary endpoints, a treatment policy strategy will be applied.

The summary measure for the co-primary variable 1 is the interval distribution, and for the co-primary variable 2 is the least square means.

2.2 Secondary estimands

Not applicable

3 Study design

This study is a 56-week, open-label, one-arm extension study in participants who have completed the CRTH258A2303 study (TALON).

[figure not shown]
Participants who consent and meet all the inclusion and none of the exclusion criteria will be enrolled into this extension study and receive brolocizumab 6 mg in a TtC regimen, irrespective of the treatment received in the core study.

Approximately 250 participants from the core study will enter the extension study. The maximum study duration for a participant is 56 weeks, including post-treatment follow-up.

There will be two periods in this study, see [Figure 3-1](#):

- Treat-to-Control treatment period: from Baseline (Day 1) to Week 52
- Post-treatment follow-up period: from Week 52 to Week 56.

Figure 3-1 Study design

Depending on visit schedules:

* 62 weeks (core) / 54 weeks (extension) ** Week 62 (core) / Week 54 (extension)

Baseline visit: Day 1

Participants should sign informed consent no later than the Week 64 (EOS) visit of the core study. Baseline visit for the extension study (extension baseline) should occur on the same day as the Week 64 (EOS) visit of the core study. Participants will be assessed on inclusion and exclusion criteria of the extension study at the baseline visit.

The study eye will be the same eye that received brolucizumab or aflibercept treatment in the core study.

Treat-to-Control treatment period: Day 1 to Week 52

All efforts should be made to adhere to the study visit schedule within a ± 14 day window (baseline visit should occur on the same day as the Week 64 (EOS) visit of the core study). For a given study visit, assessments can be performed on 2 consecutive days provided both days occur within the visit window. Study treatment is intended to be administered on the day of the study visit, or, if this is not possible, within 3 days after the assessments have taken place.

The first injection visit in the extension study will be based on the planned treatment interval as decided by the investigator at the last injection visit of the core study. The treatment interval can then be extended by 4 weeks at a time based on the investigator's judgment of visual and/or anatomic outcomes, as per guidance provided, for example, no change in visual acuity and in other signs of the disease (e.g. IRF, SRF, hemorrhage, leakage, etc.). Patients who have the last injection interval with no DA of q16w in the core study should be injected at another q16w

interval before start to extend intervals in the extension study. The maximal treatment interval is 20 weeks.

The injection interval can also be maintained if the investigator deems that the patient will not benefit from injection interval extension.

The interval should be shortened by 4 weeks at a time if DA recurs (to a minimal interval of 8 weeks).

The investigators have options to plan for an inspection visit when the treatment intervals are extended. Further details are provided in [Section 6.7.2](#).

For all participants, the last potential study treatment will be at the Week 52 visit. Participants who will receive a study treatment at an inspection visit may have a study visit at Week 54. For those participants, the Week 54 visit will take place in lieu of the visit at Week 52.

Post-treatment follow-up period: Week 52 to Week 56

For all participants completing the study, the EOS (Week 56 \pm 21 days) assessments will be performed 4 weeks after the last treatment administration (Week 52/54).

Participants withdrawn from the study prior to study completion within less than 4 weeks after the last study treatment will be asked to return for an EOS visit, 4 weeks (\pm 14 days) following their last study treatment administration (EOT). For early treatment discontinuations (ETD) refer to [Section 9.1.1](#).

4 Rationale

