4.5 Risks and benefits

The risk to participants in this trial may be minimized by compliance with the eligibility criteria and study procedures, as well as close clinical monitoring described in [Section 6.7.2](#), [Section 8.4](#) and [Section 10](#).

Adverse events (AEs) of retinal vasculitis and/or retinal vascular occlusion have occurred since the Oct-2019 marketing authorization approval for brolocizumab (Beovu®) in the treatment of nAMD. These AEs may result in severe vision loss and typically in the presence of intraocular inflammation. Based on clinical studies, IOI related adverse events, including retinal vasculitis and retinal vascular occlusion, were reported more frequently in female patients treated with brolocizumab than male patients (e.g. 5.3% females vs. 3.2% males in HAWK and HARRIER).

Results of the mechanistic study BASICHR0049 of blood samples from nAMD patients exposed to brolocizumab and having subsequently developed Retinal Vasculitis (RV) and/or Retinal Vascular Occlusion (RO), taken together with accumulated data of the association of treatment-emergent immunogenicity and intraocular inflammation (IOI), indicate a causal link between the treatment-emergent immune reaction against brolocizumab and the brolocizumab-related “retinal vasculitis and/or retinal vascular occlusion, typically in the presence of IOI”. This finding supports the requirement to discontinue treatment with brolocizumab in patients who develop events of RV and/or RO.

In addition, based on USM (CRTH258AUS04 FIR), the brolocizumab dosing interval should not be less than 8 weeks beyond the loading period.

Women of child-bearing potential must be informed that taking the study treatment may involve unknown risks to the fetus if pregnancy were to occur during the study, and agree that in order to participate in the study they must adhere to the contraception requirements outlined in the exclusion criteria. If there is any question that the participant will not reliably comply, they should not be entered or continue in the study.

In both Phase III studies (HAWK, HARRIER) in nAMD, brolocizumab demonstrated non-inferiority to aflibercept in mean change in BCVA from baseline to Week 48. These results

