6.7.2 Instruction for prescribing and taking study treatment

There will be only one treatment phase in the extension study which is similar to the TtC phase of the core study and is defined as follows:

Figure 6-1 Treatment regimen

#The treatment interval can also be maintained if the investigator deems that the patient will not benefit from treatment interval extension

*week 54, depending on visit schedule

Treat-to-Control treatment phase (Baseline/Day 1 to Week 52):

Treatment intervals will be either 8 weeks, 12 weeks, 16 weeks, or 20 weeks. A subject must be discontinued from further study treatment if treatment is required every 4 weeks.

The participant will receive the first injection based on the next planned injection interval decided by the investigator at the last injection visit of the core study. For example, if a participant has the last injection visit at Week 60 of the core study, and the next planned injection interval is a q12w interval, the first injection visit for this participant will be planned at Week 8 of the extension study (12 weeks from Week 60 of the core study).

At each injection visit, DA should be assessed using anatomic and functional outcomes (e.g. SD-OCT, BCVA, etc.). Based on investigator's judgment of visual and/or anatomic outcomes, the treatment interval can be further extended by 4 weeks at a time, if there is no DA, i.e. no change in visual acuity and in other signs of the disease (e.g. IRF, SRF, hemorrhage, leakage, etc.).

Participants whose last injection interval in the core study is q16w and are without DA should be injected at another q16w interval in the extension study before extending to q20w in the extension study.

The treatment interval can also be maintained if the investigator deems the participant will not benefit from treatment interval extension.

If DA recurs, the interval should be shortened accordingly by 4 weeks at a time, to a minimal interval of 8 weeks.

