The last potential study treatment may be administered at the Week 52 visit (or at the Week 54 visit for the participants who will have received study treatment at an odd number of inspection visits).

DA assessments will be recorded in the IRT system by the investigator or his/her delegate.

A DA assessment will also be performed at the Week 56/EOS visit; however, no study treatment will be administered.

The different types of study visits are summarized in [Table 6-3](#) with a description of when DA assessments and treatments take place.

Table 6-3 Disease Activity assessment and treatment occurrence according to visit type

Type	Study Period	DA Assessment	Treatment
Baseline visit	TtC-Phase	Yes	Only if treatment was planned according to the individual TtC regimen of the core study
Treatment visits	TtC-Phase	Yes	Yes
Inspection visits (optional)	TtC-Phase	Yes	Based on DA, as per investigator's judgement
Week 52/54*	TtC-Phase	Yes	Only if treatment was planned according to the individual TtC regimen
ETD visit and EOS visit (Week 56)	Follow-Up	Yes	No

Brolucizumab should be administered in the study eye on the day of the study visit, or, if this is not possible, within 3 days after the occurrence of the study visit (except for Baseline / Day 1, in which case study treatment administration should occur within the next 24 hours) or no later than within the visit window (± 14 days) as described in [Section 3](#) and [Section 8](#). When assessments and treatments take place on the same day, treatment must occur after completion of the efficacy assessments described in [Section 8.3](#) and pre-injection safety measures (tonometry, slit lamp and fundus examinations) described in [Section 8.4](#). If study visit assessments and the corresponding treatment occur on separate days, a repeat safety checkup should be performed prior to treatment of the eye and results should be documented in the source documents.

If any safety concern arises related to the study eye that, in the opinion of the investigator, may be further impacted by the study treatment or injection procedure, treatment needs to be cancelled.

IVT injection is contraindicated in participants with active intraocular or periocular infections and in participants with active intraocular inflammation; therefore, the investigators must verify that these conditions are not present in the study eye prior to every injection. Any adverse events must be recorded in the eCRF.

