2.1.1 General definitions

All the definitions, e.g. baseline, on-treatment period, are referring to the current extension study unless otherwise stated, e.g. baseline of the core study.

Study treatment is defined as brolocizumab 6 mg/0.05 mL.

Date of first administration of study treatment is defined as the first date when a non-zero dose of study treatment is administered and recorded on the case report form (CRF) dose administration page. The date of first administration of study treatment will also be referred to as start of study treatment.

Date of last administration of study treatment is defined as the last date when a non-zero dose of study treatment is administered and recorded on the CRF dose administration page. The last administration of study treatment will also be referred as end of treatment (EOT).

Study day will be calculated as:

- The date of the event (visit date, onset date of an event, assessment date etc.) – treatment start date + 1, if event is on or after the treatment start date;
- The date of the event (visit date, onset date of an event, assessment date etc.) – treatment start date, if event precedes the treatment start date.

Baseline/Day 1 is the end of study (EOS)/Week 64 of the core study.

On-treatment period is defined from Day 1 of the study to 30 days after the last administration of study treatment (i.e. EOT) or end of study (EOS), whichever is the latest.

Treatment interval is defined as the time period from one injection until the next injection. In this study, treatment intervals of q4w, q8w, q12w, q16w and q20w, meaning that there are 4, 8, 12, 16 and 20 weeks between 2 injections, are of special interest. The last (treatment) interval at Week X is referred to the last complete interval where injections at both ends of the interval have occurred on or before Week X. The last interval with/without disease activity is referred to the last interval with/without disease activity as observed at the end of the interval.

The first treatment is defined by the treatment interval of the core study. For example, a patient who started a 16-weeks interval at Week 56 of the core study will have the first treatment 8 weeks after the start of the extension study (i.e. 8 weeks after Week 64).

Participants will be assessed for eligibility based on inclusion and exclusion criteria for the extension study at the baseline visit.

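### The ±14-day visit window lets a q8w injection fall as early as day 42, although Protocol Sections 1.1 and 4.5 say that post-loading doses should be at least 8 weeks apart

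*Protocol*

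**What the plan says.** **The limit.** Protocol Section 1.1, citing the urgent safety measure, says that the time between two "doses should not be shorter than 8 weeks beyond the loading phase". It then calls the overall risk/benefit positive "when patients are dosed at q8w or longer after the loading phase", provided that participants who develop retinal vasculitis or retinal vascular occlusion are also taken off treatment. Section 4.5 repeats that the brolucizumab "dosing interval should not be less than 8 weeks beyond the loading period". SAP Section 2.1.1 makes the unit explicit: "Treatment interval is defined as the time period from one injection until the next injection".

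**The window.** Protocol Section 3 (Treat-to-Control treatment period) says: "All efforts should be made to adhere to the study visit schedule within a ± 14 day window". Only the baseline visit is treated differently. Section 6.7.2 repeats the ±14 days when it says that an injection not possible on the visit day should follow within 3 days "or no later than within the visit window".

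**Related text.**
- Section 6.7.2: "If DA recurs, the interval should be shortened accordingly by 4 weeks at a time, to a minimal interval of 8 weeks". Section 3 has an equivalent sentence.
- Section 8 asks that visits stay near their scheduled date.
- SAP Table 5-1 lists over-treatment and a wrongly adjusted interval among the deviations that exclude a participant from the PPS, without a day threshold.

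**The concern.** Sites schedule from the window, and its early side is as wide for q8w, the shortest permitted interval, as for q20w. A site that books a q8w injection for day 45 is inside the Section 3 window and below the limit in Sections 1.1 and 4.5, and cannot tell from the protocol whether it complies.

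The lines about a minimal 8-week interval do not settle this. They limit how far the planned interval may be shortened when disease activity recurs; they do not address how early a planned q8w visit may take place. Section 8 discourages early visits but sets no floor. At stake is whether the scheduling rule protects the limit that the plan adopted for safety.

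**Working it through.** **Inputs.** Shortest planned interval 8 weeks (Protocol Section 6.7.2) = 56 days. Window ±14 days (Section 3). Stated minimum between doses 8 weeks = 56 days (Sections 1.1 and 4.5).

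**Where an interval starts.** The documents' own scheduling examples count from the previous injection, and both reproduce:
- Protocol Section 6.7.2: core Week 60 + 12 − 64 = extension Week 8.
- SAP Section 2.1.1: core Week 56 + 16 − 64 = extension Week 8.

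Table 8-1, footnote 2, also counts inspection visits from the last injection. Section 3, however, attaches the window to the visit schedule, so a fixed-calendar reading is possible as well.

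**Earliest in-window gap for a visit planned w weeks after the last injection.**
- Counted from the previous injection: 7w − 14 days.
- Against fixed calendar weeks, with the previous injection 14 days late and this one 14 days early: 7w − 28 days.

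| Visit | Planned (days) | From previous injection | Fixed calendar |
|---|---|---|---|
| q8w | 56 | **42** | **28** |
| 10-week inspection | 70 | 56 | **42** |
| q12w | 84 | 70 | 56 |
| 14-week inspection | 98 | 84 | 70 |
| q16w, or 16-week inspection | 112 | 98 | 84 |
| q20w | 140 | 126 | 112 |

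Bold entries are below 56 days. On the first reading only q8w is affected, by up to 56 − 42 = 14 days (14/56 = 25%). On the second, q8w can be 28 days short and a 10-week inspection injection 14 days short.

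**Who is exposed.** The simulations in Protocol Table 12-2 put 30.2% of participants on 8 weeks, or 0.302 × 250 ≈ 76 people. They predate the urgent safety measure, so this is only indicative. It says who is scheduled under the window, not how many injections would be early.

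**With a 56-day floor.** The q8w window becomes 56 to 70 days. Counted from the previous injection, no other visit type changes. On the calendar reading the floor also catches the 10-week inspection injection.

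**What the floor does to a participant on q8w throughout.** Seven injections span 6 × 56 = 336 days.
- First extension injection at Week 0: the seventh is due at Week 48, and 364 − 336 = 28 days remain to Week 52. A mean delay of up to 28/6 = 4.7 days per interval still fits all seven.
- First extension injection at Week 4: 28 + 336 = 364 days, exactly Week 52. Only that visit's own +14 days is spare, a mean of 14/6 = 2.3 days per interval.

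**The case against.** The strongest reply is that 8 weeks means the assigned regimen. Section 6.7.2 offers discrete intervals of 8, 12, 16 or 20 weeks, the safety signal came from a q4w regimen, and the binding instruction is to stop treatment when q4w dosing is needed. On that view a participant assigned q8w and seen a few days early is still on q8w, and a tolerance around a nominal interval is ordinary practice. The limit itself is worded as a recommendation in background and risk sections. This reading is plausible, but the protocol nowhere states it, and it fits poorly with Section 1.1, which speaks of the time between two doses.

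Three further points stand in part:
- The Section 6.7.2 sentence that repeats the window mainly governs postponement. It is weak support for early injections, so Section 3 carries the point.
- Unseen controls may exist. The IRT issues a kit at each treatment and may already check dates, and the deviation thresholds sit in other documents. The deviations listed in the SAP, though, act on the PPS after the injection and give sites no minimum.
- A floor has a clinical cost: later dosing in the eyes that need the shortest interval may let disease activity recur.

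Stronger inferences are tempting but unsupported:
- That about half of q8w injections would be early, because days 42 to 55 are 14 of the 29 in-window days (42 to 70). This counts calendar days, not likelihood; visits should cluster near the target.
- That a 6-week gap carries the risk seen with q4w dosing. The documents report nothing on gaps of 42 to 55 days.
- That early injections would corrupt the durability endpoint. The footnote to Protocol Table 12-1 and SAP Table 2-1 maps lengths from q4w up to q8w to q4w, so a literal reading would count a 42-to-55-day last interval as q4w. SAP Section 2.6.3 ties that rule to treatment interruption, so the effect depends on programming that is not shown.

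**Conclusion.** The point holds as a mismatch in current text: the stated safety limit is 56 days between doses, and the visit window allows 42 days when counted from the previous injection, with no minimum stated anywhere. The fixed-calendar reading lowers this to 28 days for q8w and 42 days for a 10-week inspection injection. The conclusion rests on taking Section 1.1 at its word, as a dose-to-dose limit, and on the absence of a day minimum from these two documents; it cannot exclude a check inside the IRT.

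Harm is not shown, because neither the frequency of early injections nor the risk of a 6- to 8-week gap can be derived. No estimate, endpoint or test is shown to be wrong. This is a cheap improvement worth considering, not a defect that threatens the trial's conclusions.

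**What to change.** In Protocol Sections 3 and 6.7.2, add that no study injection is given less than 56 days after the previous injection, whatever the visit window. For q8w this means a window of 0 to +14 days; longer intervals keep ±14 days, subject to the same floor. Apply the check in the IRT, which Section 6.6.1 already requires sites to access at every visit, and report the number of injections given at under 56 days. If the sponsor does intend a tolerance below 56 days, Sections 1.1 and 4.5 should say so instead.

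The direct cost is one sentence in each of two sections and a date check. The downside is that q8w visits can only move later, so a delay cannot be made up and treatment may be late in eyes that need the shortest interval. A participant whose first extension injection is at Week 4 may lose the last injection. The Week 52 visit itself is kept, because Section 6.7.2 requires it whether or not treatment is given.
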